9.1 Adverse Events

An **adverse event** (AE) is any untoward medical occurrence in humans, whether or not considered drug-related, which occurs during the conduct of a clinical trial. (Any change in clinical status, routine labs, x-rays, physical examinations, etc.), that is considered clinically significant by the study investigator is considered an AE.

Suspected adverse reaction is any adverse event for which there is a reasonable possibility that the drug caused the adverse event. A reasonable possibility implies that there is evidence that the drug caused the event.

Adverse reaction is any adverse event caused by the drug.

Serious adverse event or serious suspected adverse reaction or serious adverse reaction as determined by the investigator or the sponsor is any event that results in any of the following outcomes:

1. Death at or before 36 weeks PMA

2. Life-threatening AE (“life-threatening” means that the study participant was, in the opinion of the investigator or sponsor, at immediate risk of death from the reaction as it occurred and required immediate intervention)
3. Persistent or significant incapacity or substantial disruption of the ability to conduct normal life functions
4. Inpatient hospitalization or prolongation of existing hospitalization
5. Important medical event that may not result in one of the above outcomes, but may jeopardize the health of the study participant or require medical or surgical intervention to prevent one of the outcomes listed in the above definition of serious event

All AEs will be coded using the Medical Dictionary for Regulatory Activities (MedDRA) central coding dictionary. All AEs and SAEs will be summarized by dose groups.

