1.1 Study Synopsis

Protocol Title	Safety of Furosemide in Premature Infants at Risk of Bronchopulmonary Dysplasia (BPD)
Phase:	II
Protocol Version	Version 5.0, 7 April 2015
Product	Furosemide
Objective	Primary: Describe the safety of furosemide in premature infants at risk of BPD Secondary: Preliminary effectiveness and pharmacokinetics (PK) of furosemide
Study Design	Multi-center, randomized, placebo-controlled, dose escalating, double masked, safety study

Study Population	
Inclusion Criteria
 
 1. Documented informed consent from legal guardian, prior to study procedures 2. Receiving positive airway pressure (nasal continuous airway pressure, nasal intermittent positive pressure ventilation, or nasal cannula flow > 1LPM) or mechanical ventilation (high frequency or conventional) 3. < 29 weeks gestational age at birth 4. 7-28 days postnatal age at time of first study dose 
Exclusion Criteria
 
 1. Exposure to any diuretic ≤ 72 hours prior to first study dose 2. Previous enrollment and dosing in current study, “Safety of Furosemide in Premature Infants at Risk of Bronchopulmonary Dysplasia” 3. Hemodynamically significant patent ductus arteriosus, as determined by the investigator 4. Major congenital anomaly (e.g. congenital diaphragmatic hernia, congenital pulmonary adenomatoid malformation) 5. Meconium aspiration syndrome 6. Known allergy to any diuretic 7. Serum creatinine >1.7 mg/dl < 24 hours prior to randomization 8. BUN >50 mg/dl < 24 hours prior to randomization 9. Na <125 mmol/L < 24 hours prior to randomization 10. K ≤2.5 mmol/L < 24 hours prior to randomization 11. Ca ≤ 6 mg/dL < 24 hours prior to randomization 12. Indirect bilirubin >10 mg/dl < 24 hours prior to randomization 13. Any condition which would make the participant, in the opinion of the investigator, unsuitable for the study 																												
Number of Participants	120																												
Number of Sites	Approximately 30 sites																												
Duration of Participation:	Up to 35 days (28 days of study drug plus 7 days of safety monitoring). Information about hospitalization will be collected at 36 weeks post menstrual age and/or at discharge.																												

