8.2 Demographics and Baseline Characteristics

Demographic and baseline characteristics will be collected during the screening visit. Variables include gestational age (GA) at birth, postnatal age (PNA), post menstrual age (PMA), maternal race, maternal ethnicity, sex, and birth weight. The PMA is calculated by adding up the completed weeks of GA and PNA. Also, respiratory assessment will be conducted at baseline visit. Surfactant therapy administration and antenatal betamethasone use by the participant's mother will also be summarized.

Medical history will be MedDRA coded and summarized by system organ class and preferred term. Medical history will also be summarized in a participant listing which will also include the actual reported medical conditions. The listing will also include system organ class, preferred term and onset date.

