9 SAFETY ANALYSES

Safety will be assessed following initial study-specific procedure e.g., screening blood draws, dosing through 7 days post last study dose and will be assessed by frequency and incidence of all AEs and SAEs. Other safety parameters include clinical laboratory measurements of interest, concomitant medications of interest, physical examination abnormalities and special events of interest: hearing loss, nephrocalcinosis/nephrolithiasis, and respiratory assessment.

Safety summaries will be provided by dose groups based on data from pre-dose and post-dose visits for the safety population. Frequency counts and descriptive statistics will be provided.

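### The death criterion for a serious event stops at 36 weeks PMA, but the safety window of a few late-starting infants can run past that age

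*SAP*

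**What the plan says.** SAP Section 9.1 uses one list of outcomes for three terms: "Serious adverse event or serious suspected adverse reaction or serious adverse reaction as determined by the investigator or the sponsor". Item 1 of that list, and the only item that names death as an outcome, is "Death at or before 36 weeks PMA".

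Section 9 sets the period of safety assessment differently: "Safety will be assessed following initial study-specific procedure e.g., screening blood draws, dosing through 7 days post last study dose". It gives no PMA limit.

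The Study Synopsis (Section 1.1) sets the calendar. Infants must be "< 29 weeks gestational age at birth" and "7-28 days postnatal age at time of first study dose". Participation is "Up to 35 days (28 days of study drug plus 7 days of safety monitoring". Nothing in the SAP ends dosing or adverse-event collection at 36 weeks PMA.

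The only statement on computing PMA is in Section 8.2, among the baseline variables: "The PMA is calculated by adding up the completed weeks of GA and PNA".

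**The concern.** The death criterion is tied to a fixed age and the safety window to the last dose. For an infant who starts late and was born near the upper gestational-age limit, the age cutoff comes first. A death after it lies inside the safety window but fails the one criterion that would make it serious without further judgement. It could still qualify under criterion 2 (immediate risk of dying, with immediate intervention needed) or criterion 5 (an important medical event). Both rest on an assessment of the event, not on the fact of death.

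Two outputs depend on this:

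- **Reporting.** Adverse events are the primary outcome (Section 2.2.1). Section 13 lists no table or listing devoted to deaths. A late death not classed as serious would be missing from the serious adverse event table (14.3.1.3) and, if caused by the drug, from the serious adverse reaction table (14.3.1.4).
- **Escalation.** Section 4.1 pauses the trial at 4 Serious Adverse Reactions in a cohort. Below that, the share of safety days required before the next cohort opens rises with each one: 70%, 80%, 95% and 100% for 0, 1, 2 and 3. A single event can move the requirement.

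**Working it through.** **Inputs.** Upper gestational age (GA) at birth 28w6d = 202 days; first dose on postnatal day 7 to 28; 28 days of drug plus 7 of monitoring (all Section 1.1); window to 7 days after the last dose (Section 9). The plan's own total reproduces: 28 + 7 = 35 days.

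**Formulas.**

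- PMA at last dose = GA + day of first dose + 27, counting the first dosing day as day 1. Adding 28 instead gives the other end of each range below.
- PMA at end of window = PMA at last dose + 7.
- 36w0d = 36 × 7 = 252 days. The last day of that completed week, 36w6d, is 258 days.

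**Latest case.** GA 28w6d, first dose on day 28:

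- first dose: 202 + 28 = 230 days = 32w6d
- last dose: 230 + 27 = 257 days = 36w5d
- end of window: 257 + 7 = 264 days = 37w5d
- excess over 36w0d: 264 − 252 = 12 days (13 with +28)
- excess over 36w6d: 264 − 258 = 6 days (7 with +28)

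**Who is reached, on the 36w0d reading.** With a first dose on day 28, the window passes 252 days when GA + 28 + 34 > 252, so GA of at least 191 days (27w2d). At GA 28w6d it passes when the first dose falls on day 17 or later. Dosing itself passes 36w0d only from GA 28w2d with a day-28 start, or from day 24 at GA 28w6d.

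**Share of combinations.** The SAP gives no distribution of GA or entry age. As an assumption, take every GA from 23w0d to 28w6d (42 days) with every first-dose day from 7 to 28 (22 days), equally weighted: 42 × 22 = 924 combinations. The lower limit of 23 weeks is also assumed. Each range covers the two ways of counting the last dose.

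| Reading of the cutoff | Window passes it | Dosing passes it |
|---|---|---|
| Exact days, 36w0d | 78-91 of 924 (8.4-9.8%) | 15-21 of 924 (1.6-2.3%) |
| Exact days, through 36w6d (completed weeks of the combined age) | 21-28 of 924 (2.3-3.0%) | 0 |
| GA weeks and postnatal weeks rounded down separately, then added | 0-7 of 924 (0-0.8%) | 0 |

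In the third row the latest case gives 28 completed weeks of GA plus 8 of postnatal age (day 62), which is 36 weeks. If the window ends one day later (day 63), it is 28 + 9 = 37.

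**Share of window days.** On the 36w0d reading, 364 of 924 × 35 = 32,340 window days fall after the cutoff (1.1%), or 455 of 924 × 36 = 33,264 with the longer count (1.4%). Through 36w6d the figures are 56 of 32,340 (0.2%) and 84 of 33,264 (0.3%).

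**The case against.** **The gap depends on an unstated convention.** Section 8.2 adds completed weeks of GA and of postnatal age. If each is rounded down first, the worst case is still at 36 weeks when the window closes, and the gap closes or shrinks to one day. This stands as a limit on the size. It does not dispose of the point: Section 8.2 concerns baseline variables, its wording also allows rounding down the combined age, and criterion 1 does not say how its cutoff is computed.

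**Other criteria would catch most such deaths.** A fatal event will usually have put the infant at immediate risk or count as an important medical event, and seriousness is for the investigator or the sponsor to determine. Any such event remains an adverse event, and Section 2.2.3 assesses death separately with no age limit. This also stands. What remains is that these routes need a judgement that a death should not need.

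**The halting counts are unlikely to move.** They count reactions caused by the drug. To be missed, a drug-caused death would have to fall in the last days of a late starter's window and be judged to meet neither criterion 2 nor criterion 5. That is possible but rare.

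**Stronger readings the text does not support.** A reader might infer that the two sections contradict each other. They do not: one says when safety is assessed, the other what makes an event serious, and both can be applied together. A reader might also infer that 8-10% of infants are affected. That figure is a share of cells on an assumed grid. Nor is it settled that dosing runs past the cutoff; that holds only if 36 weeks means 36w0d.

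**Conclusion.** The mismatch in coverage is real but small. On exact-day PMA, and on completed weeks of the combined age, a death inside the Section 9 window can fall outside the only death criterion for seriousness. Only infants near the upper GA limit who start late are exposed. For the large majority of combinations the cutoff falls at or after the end of the window, so criterion 1 matches or extends death capture there.

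The sizes rest on the uniform grid, the assumed 23-week lower limit and full 28-day dosing. Shorter courses would reduce them. The SAP shows no actual case and no effect on a halting or cohort-advance decision. The change is still worth making: adverse events are the primary outcome, the same list defines the reactions counted in Section 4.1, and the correction is short.

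**What to change.** Reconcile criterion 1 with Section 9, in line with the protocol definition. Suggested wording: death from the first study procedure through the later of 36 weeks PMA and 7 days after the last study dose. This keeps the longer capture that most infants already have and removes the shortening for the few.

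State that every such death is counted as serious in the SAE outputs and, when judged caused by the drug, in the Serious Adverse Reaction outputs and the Section 4.1 counts. State also how PMA is computed for the cutoff: exact days, completed weeks of the combined age, or the sum of separately completed weeks.

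The cost is a line or two of SAP text and a check against the protocol. Sample size and precision do not change. Sites presumably assign seriousness under the protocol, which is not at hand. A SAP edit alone may therefore not reclassify events already recorded, so any death in the affected days should be checked by date of death, date of last dose and PMA before database lock.

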2.2 Outcomes

2.2.1 Primary Outcome Measures

Safety as determined by adverse events experienced by the participants.

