4 ANALYSES AND REPORTING

4.1 Dose Escalation and Halting Criteria

The trial will be halted (paused) for a safety review by the Data Monitoring Committee (DMC) if there are 4 or more Serious Adverse Reactions within a given Cohort (i.e., Cohort 1, 2, or 3). If there are <4 Serious Adverse Reactions total, the DMC will receive a summary of masked safety data and enrollment will continue in the next highest dose Cohort. Enrollment in the next highest dose Cohort will begin immediately after the 40th (or 80th) subject is enrolled and the following criteria have been met:

Table 1 Rules for advancing to next highest dose Cohort

Number of Serious Adverse Reactions	% total evaluable safety days* completed from lower dose Cohort
3	100%
2	95%
1	80%
0	70%

*% total evaluable safety days = $\frac{\text{sum of days of dosing} + 7 \text{ days of safety follow up for all participants}}{\# \text{ of participants} \times 35}$

If a 4th Serious Adverse Reaction occurs in the lower dose Cohort after enrollment begins in higher dose Cohort, enrollment will be halted for safety review but current subject dosing will continue pending DMC review. If there are 4 or more Serious Adverse Reactions, then the DMC may choose to be unmasked to treatment assignment.

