4.2 Interim Analyses

A masked interim safety analysis will be performed after completion of the safety follow up period of Cohort 1 participants, and again after completion of the safety follow up period of Cohort 2 participants to include data entered up to the cutoff time point (data from next Cohort will be included if entered before the cutoff time point). Enrollment will not be halted during the analyses. Halting may occur if analysis shows a positive finding. The number and percent of AEs and SAEs within each dose group will be summarized overall as well as by each Medical Dictionary for Regulatory Activities (MedDRA) system organ class and preferred term. BPD, nephrocalcinosis/nephrolithiasis, and hearing loss will be included in the summary. Also, laboratory adverse events will be tabulated by cohort.

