8 STUDY PARTICIPANTS AND DEMOGRAPHICS

8.1 Disposition of Participants and Withdrawals

All safety participants will be accounted for in this study. Number and percentage by Cohorts and dose groups for the safety population and PK population will also be presented. Also, summaries will include the number and percentage of participants who completed or early terminated the study, classified by reasons for early termination; the number of participants from each study site; and the number and percentage of participants who completed or early terminated the study at each study site. Early termination is defined as:

1. Participant is randomized but does not receive at least 7 days of study product.

2. Participant receives 7-28 days of study product, but does not complete required follow up assessments.

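### AE and SAE summaries by dose group take no account of time at risk, which can run from about 8 to 35 days, and no table shows exposure

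*SAP*

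**What the plan says.** Section 2.2.1 sets the primary outcome: "Safety as determined by adverse events experienced by the participants". Section 9 starts safety assessment at the first study-specific procedure, such as screening bloods, and continues it through "dosing through 7 days post last study dose and will be assessed by frequency and incidence of all AEs and SAEs". The form of the final summary is "Frequency counts and descriptive statistics will be provided" (section 9) and "All AEs and SAEs will be summarized by dose groups" (section 9.1). The one place that spells out the form is section 4.2, for the interim: "The number and percent of AEs and SAEs within each dose group will be summarized overall". Section 6 puts every randomized and dosed infant in the safety population, whatever the length of dosing.

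The synopsis gives participation as "Up to 35 days (28 days of study drug plus 7 days of safety monitoring". Section 8.1 defines early termination in two ways: under 7 days of study product, or "Participant receives 7-28 days of study product, but does not complete required follow up assessments". An infant dosed for 7 days and an infant dosed for 28 days, both with follow-up done, are therefore both completers.

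Section 4.1 adds up time under observation, using the "sum of days of dosing" plus 7 days of follow-up, but only to decide when the next cohort may open. In section 13, no table reports dosing duration or days at risk. The dosing listing (16.2.6) is marked as supporting no table; only the patient-profile figure (14.4.3) cites it.

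**The concern.** A proportion with at least one AE depends on how long each infant is watched as well as on how often events occur. Here the length of watching is tied to the length of dosing. Suppose infants in one dose group come off study drug sooner than those in another, for whatever reason. Their windows close sooner, and events that would have fallen later are not collected as general AEs or SAEs. The crude percentage then understates risk in that group relative to the others.

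Describing safety by dose is the trial's main purpose, so these are the figures readers will compare across groups. As planned, they could not tell from the tables whether two groups with similar percentages were observed for similar times.

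**Working it through.** **Inputs from the SAP.** Maximum window 28 + 7 = 35 days (synopsis). Dosing of 7 to 28 days, or under 7 days (section 8.1). Thirty infants per dose group (section 5). The SAP gives no daily event rate, 35-day risk or stopping pattern, so those below are assumptions.

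**Step 1: the SAP's own figures.** Section 5 gives a 79% chance of seeing an event of incidence 0.05 at least once in 30 infants, and 99% in 90. By formula, 1 − 0.95^30 = 0.785 and 1 − 0.95^90 = 0.990. The 95% Wilson widths at rates 0.1, 0.2 and 0.3 come out as 0.222, 0.278 and 0.312 for n = 30 and 0.126, 0.164 and 0.186 for n = 90, which match Table 2. All are binomial calculations with one common risk per infant, and so take observation time as the same for everyone.

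**Step 2: range of the window from first dose.**
- 1 dosing day: 1 + 7 = 8 days
- 7 dosing days: 7 + 7 = 14 days
- 28 dosing days: 28 + 7 = 35 days

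Two completers can thus differ by 35/14 = 2.5-fold.

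**Step 3: effect on one infant's risk.** Assume a constant daily hazard and a 35-day risk of 30%. Then h = −ln(0.70)/35 = 0.01019 per day, and the risk over T days is 1 − exp(−hT):

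| Window (days) | 8 | 14 | 21 | 28 | 35 |
|---|---|---|---|---|---|
| Crude incidence | 7.8% | 13.3% | 19.3% | 24.8% | 30.0% |

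The daily rate is the same in every column.

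**Step 4: effect on a dose group.** Let a share f of the group stop at day 7 (14-day window) and the rest complete 28 days. Crude incidence = f × 13.30% + (1 − f) × 30%. Total window days for 30 infants = 30 × [14f + 35(1 − f)], against 30 × 35 = 1050. The last column is the hazard ratio at which the shortened group would still show a crude 30%, that is, the excess that equal percentages would hide.

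| f | Crude incidence | Shortfall (points) | Window days | Hidden hazard ratio |
|---|---|---|---|---|
| 10% | 28.3% | 1.7 | 987 | 1.07 |
| 20% | 26.7% | 3.3 | 924 | 1.15 |
| 30% | 25.0% | 5.0 | 861 | 1.25 |
| 50% | 21.6% | 8.4 | 735 | 1.48 |

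A first-event rate per day at risk is 1.02 per 100 infant-days in every row, because h is unchanged.

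**Step 5: effect on detection, as a limiting case.** If 0.05 is a 35-day risk and all 30 infants in a group had a 14-day window, the risk per infant would be 1 − 0.95^(14/35) = 2.0%. The chance of at least one event would be 1 − 0.95^(0.4 × 30) = 46%, against the 79% stated.

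**The case against.** Several counter-arguments are sound and limit the point.

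- **No difference in duration is shown.** Bias between doses needs dosing duration to differ by group, and the SAP neither states nor implies that it will. A reader might infer that a dose stopped early will look safer than it is. The document does not support that as a fact; it holds only if durations differ.
- **Dramatic examples are easy to build.** Take a dose that doubles the hazard, with every infant stopped at day 10 (17-day window), against placebo infants who all complete. Crude incidence is then 1 − exp(−2h × 17) = 29.3% against 30%, and a reader might conclude that a true ratio of 2.0 appears as 0.98. That compares a risk ratio with a rate ratio. With equal 35-day windows, doubling the hazard gives 1 − 0.70² = 51% against 30%, a risk ratio of 1.70, so part of the gap is a change of scale. The scenario is also extreme.
- **An AE that leads to stopping is already counted.** Only later or different events in that infant are lost, and fewer are lost if the hazard falls off drug.
- **Other safety data run longer.** Death is serious up to 36 weeks PMA (9.1), laboratory values are summarized at 36 weeks PMA (9.2), and hearing tests and renal ultrasound come late (9.5). The point concerns general AEs and SAEs.
- **Imprecision may dominate.** At a rate of 0.3 with 30 infants, the Wilson interval is 31 points wide, against shortfalls of 1.7 to 8.4 points above.
- **Some stopping is visible.** Dosing under 7 days appears as early termination, and profiles plot dosing and AEs for each infant.
- **Form of the final summary.** Number and percent is explicit only for the interim; for the final analysis it is inferred from the wording on frequency, incidence and counts.

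What remains is that stopping between day 7 and day 28 with follow-up done is in no table, and individual profiles are no substitute for group exposure. A descriptive aim does not remove the problem, because percentages over unequal and unreported windows can still mislead.

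**Conclusion.** The point holds as a gap in the primary safety summary, worth closing because it is cheap to close; it is not a demonstrated bias. The SAP fixes a window of variable length, reports counts and incidence without regard to it, and plans no table from which exposure by dose group can be read.

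The direction of any distortion is clear: the group observed for less time has its risk understated. Its size cannot be fixed from the document. Under a constant hazard, a 35-day risk of 30% and stopping unrelated to earlier events, the shortfall is 1.7 points if 10% of a group stop at day 7, 5.0 points if 30% do and 8.4 points if 50% do. If durations turn out alike across groups, the comparison between doses is unaffected and the added rows will show that.

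**What to change.** In section 9.1 and Table 14.3.1.1, keep the percentages and add by dose group:

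1. Dosing duration, and total observed days from first dose to the earliest of last dose + 7 days, death or loss to follow-up.
2. Either the cumulative incidence of a first AE and of a first SAE by day since first dose, or first events per 100 infant-days. For the rate, each infant's days stop at the first event.
3. A rule that only events with onset inside that same window enter item 2. AEs before the first dose and deaths after the window are reported separately.

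The safety-day sum in section 4.1 should not be taken over unchanged as the denominator. It credits each infant with 7 full follow-up days, omits the pre-dose period in which AEs are already assessed, and does not extend to 36 weeks PMA, up to which deaths count as serious.

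The cost is SAP wording and a few table rows, from dosing and event data already listed; no visit or treatment changes. The downside is that a rate per day assumes a roughly constant hazard, which is why the percentages stay beside it. Cumulative incidence avoids that assumption, but it still treats infants whose window closed early as similar to those still observed.
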